7.0 Statistical Consideration

This is an open label, phase I/II clinical trial to evaluate the safety and efficacy of lenalidomide, thalidomide, and dexamethasone in patients with relapsed/refractory multiple myeloma. The maximum number of patients that will be recruited for the study is 64.

Phase I design:

The objective of the phase I portion is to determine the maximum tolerated dose (MTD) of the combination regimen of lenalidomide, thalidomide, and dexamethasone. There are four predefined dose levels for lenalidomide, thalidomide, and dexamethasone, and the first cohort of patients will be treated at the second dose (Dose Level 1).

Dose Level	Assigned Therapy
Level -1	15 mg Lenalidomide daily on days 1-21 followed by 7-day rest every 28 days 50 mg Thalidomide daily 40 mg dexamethasone *
Level 1	15 mg Lenalidomide daily on days 1-21 followed by 7-day rest every 28 days 100 mg Thalidomide daily 40 mg dexamethasone *
Level 2	25 mg Lenalidomide daily on days 1-21 followed by 7-day rest every 28 days 100 mg Thalidomide daily 40 mg dexamethasone *
Level 3	25 mg Lenalidomide daily on days 1-21 followed by 7-day rest every 28 days 200 mg Thalidomide daily 40 mg dexamethasone

Dose limiting toxicity (DLT) is defined as in the treatment plan. To find the MTD, a statistical design based on a Bayesian model described in Ji, Li, and Bekele (2006) will be used. The details of the design are described below.

Let p_i denote the toxicity probabilities for dose $i=1, 2, 3, \text{ and } 4$. The goal is to accurately estimate the probability of toxicity at the current tried dose level. Assuming a vague independent beta prior $B(0.005, 0.005)$ for each p_i , with observed data (n_i, x_i) , where n_i represents the number of patients treated at current dose and x_i represents the number of patients experienced DLTs, the posterior of p_i follows an independent $B(0.005 + x_i, 0.005 + n_i - x_i)$ for $i=1, 2, 3, \text{ and } 4$. Let

$$T_i = 1\{P(p_i > p_T \mid \text{data}) > \xi\}$$

We define the posterior probabilities of three possible actions as

$$q(D, i) = P(p_i > p_T + K_1 \sigma_i \mid \text{data})$$

$$q(S, i) = P(p_T - K_2 \sigma_i \leq p_i \leq p_T + K_1 \sigma_i \mid \text{data})$$

$$q(E, i) = P(p_i < p_T - K_2 \sigma_i \mid \text{data}) * (1 - T_i)$$

where D represents the action of de-escalating to next lower level, S represents staying at current dose and E represents escalating to next higher level, and σ_i is the posterior deviation of p_i . The dose-assignment rule B_i is defined as $B_i^{(e)} = \arg \max_{m \in \{D, S, E\}} q(m, i)$.

[figure not shown]
Based on dose-assignment rule $B_i^{(e)}$, a dose-finding algorithm is proposed as follows:

- 1) Suppose that Dose 1 is a dose that has been tried previously. If $T_i = 1$, terminate the trial due to excessive toxicity. Otherwise, terminate the trial when the maximum sample size is reached.
- 2) At current tried dose i , the decision to select the dose for next cohort are among $\{(i-1), i, (i+1)\}$ based on the assignment rule. There are two exceptions, however: if $i=1$, the next available doses are $\{1, 2\}$; if $i=4$, the next available doses are $\{3, 4\}$.
- 3) At the end of the trial, the dose with the smallest absolute value of (*posterior mean of $p_i - p_T$*) among all the tried doses i for which $T_i=0$ will be selected as the MTD.

Let $\xi = 0.95$, $K_1=1$ and $K_2=1.5$. Starting at Dose Level 1 (the second dose), the trial will enrol patients in a cohort size of three. The maximum sample size is 18 and the MTD has a probability of toxicity $p_T=0.4$. Table 1 presents the monitoring rules for each dose and Table 2 presents the operating characteristics of the proposed design under six toxicity scenarios. When MTD is among the doses studied (Scenarios 1, 2, and 3), this dose will be selected with the highest probability and the number of patients treated at this dose will be the largest among all doses. If all the Dose levels turn out to be too toxic (Scenario 6), the chances of these doses being selected are very low and most of the few patients treated will be at the lowest dose level. On the other hand, if all the Dose levels are below the MTD (Scenario 5), the highest dose will be chosen with the highest probability and most patients will be treated at the highest dose.

Table 1. Dose-finding trail-monitoring chart

		Number of patients treated at current dose																	
		1	2	3	4	5	6	7	8	9	10	11	12	13	14	15	16	17	18
Number of toxicities	0	E	E	E	E	E	E	E	E	E	E	E	E	E	E	E	E	E	E
	1	D U	S	S	S	E	E	E	E	E	E	E	E	E	E	E	E	E	E
	2		D U	S	S	S	S	S	S	E	E	E	E	E	E	E	E	E	E
	3			D U	D	S	S	S	S	S	S	S	S	E	E	E	E	E	E
	4				D U	D	D	S	S	S	S	S	S	S	S	S	E	E	E
	5					D U	D	D	D	D	S	S	S	S	S	S	S	S	S
	6						D U	D	D	D	D	D	S	S	S	S	S	S	S
	7							D U	D	D	D	D	D	D	S	S	S	S	S
	8								D U	D	D	D	D	D	D	D	S	S	S
	9									D U	D	D	D	D	D	D	D	D	S
	10										D U	D	D	D	D	D	D	D	D
	11											D U	D	D	D	D	D	D	D
	12												D U	D	D	D	D	D	D
	13													D U	D	D	D	D	D
	14														D U	D	D	D	D
	15															D U	D	D	D
	16																D U	D	D
	17																	D U	D
	18																		D U

E = Escalate to next higher dose

S = Stay at current dose

D = De-escalate to next lower dose

U = Current dose is unacceptable

Table 2. Operating characteristics

Scenario		Dose -1	Dose 1	Dose 2	Dose 3	Total # of Pts	Overall Toxicity
1	Toxicity Rate	0.4	0.55	0.65	0.65	17.568	0.535121
	Chance Selected	0.507	0.313	0.08	0.015		
	# of Pts Treated	5.799	6.069	5.322	0.378		
2	Toxicity Rate	0.05	0.1	0.4	0.6	18	0.366222
	Chance Selected	0.002	0.17	0.703	0.125		
	# of Pts Treated	0.432	3.321	11.718	2.529		
3	Toxicity Rate	0.05	0.1	0.15	0.4	18	0.287222
	Chance Selected	0	0.003	0.232	0.765		
	# of Pts Treated	0.012	0.48	7.164	10.344		
4	Toxicity Rate	0.2	0.35	0.55	0.6	17.979	0.435675
	Chance Selected	0.12	0.53	0.322	0.025		
	# of Pts Treated	2.073	7.074	7.941	0.891		
5	Toxicity Rate	0.05	0.1	0.15	0.2	18	0.184056
	Chance Selected	0	0.005	0.114	0.881		
	# of Pts Treated	0.03	0.315	5.991	11.664		
6	Toxicity Rate	0.5	0.6	0.65	0.7	17.16	0.574242
	Chance Selected	0.492	0.233	0.078	0.004		
	# of Pts Treated	6.216	5.283	5.388	0.273		

Phase II design:

During the phase II portion of the study, patients will be treated with lenalidomide, thalidomide, and dexamethasone in combination at the MTD established in the phase I portion. Furthermore, the patients treated at the MTD in the phase I portion of the study will be considered the first patients of the phase II portion. It is anticipated that at least 6 patients will be treated at the MTD in the phase I and will be later included in the analysis of the phase II portion.

Response will be assessed after 4 cycles of therapy.

The overall response and toxicity will be monitored simultaneously using the Bayesian approach of Thall, Simon, Estey (1995, 1996) as extended by Thall and Sung (1998). Historical data on similar patients show an overall response rate (ORR) of 30% and toxicity rate of 30%. However, the information was down-weighted to reflect the same marginal ORR and toxicity rates in 2 patients. Independence was assumed between OR and toxicity. It is expected for the current trial that the three-drug combination will improve the ORR to 50% while the toxicity rate is maintained at 40%. A sample size of 36 ensures that, if the trial is not terminated early, a posterior 90% credibility interval for overall response rate will have width of 0.26 at most, under the assumption of a 50% of ORR. The probabilities of OR and toxicity for the historical data are modeled by beta distributions ($Beta(3, 7)$ and $Beta(3, 7)$, respectively). The prior probabilities of OR and toxicity for the experimental regimen are also modeled by beta distributions ($Beta(0.6, 1.4)$ and $Beta(0.6, 1.4)$, respectively), which have the same a/b (a and b denote the parameters for a $Beta$ distribution) ratio as the beta distributions for the historical data. Denoting the historical probabilities of overall response rate and toxicity rate by $\{p(OR,H), p(TOX,H)\}$, the following decision criteria will be applied:

- 1) Let E correspond to the experimental treatment, stop if $\text{Prob}\{p(OR,H) + \delta_{OR} > p(OR,E) | \text{data}\} > 0.90$, where $\delta_{OR} = 0.20$
- 2) Stop if $\text{Prob}\{p(TOX,H) + \delta_{TOX} < p(TOX,E) | \text{data}\} > 0.85$, where $\delta_{TOX} = 0.10$

Patients will be monitored according to the following stopping boundaries for overall response.

Number of patients evaluated	Recommend stopping if \leq OR observed
12	3
24	7
36	11

At the same time, patients will be monitored according to the following stopping boundaries for toxicity.

Among these number of patients	Recommend stopping if \geq toxicity observed
12	8
24	15
36	22

The operating characteristics are summarized in the following table (based on simulations from 10,000 trials).

True Toxicity Rate	True OR Rate	Prob(stop the trial early)
0.1	0.3	0.654
	0.4	0.296
	0.5	0.086

	0.6	0.016
	0.7	0.002
0.25	0.3	0.655
	0.4	0.298
	0.5	0.089
	0.6	0.019
	0.7	0.005
0.4	0.3	0.677
	0.4	0.343
	0.5	0.147
	0.6	0.082
	0.7	0.068
0.55	0.3	0.795
	0.4	0.583
	0.5	0.225
	0.6	0.417
	0.7	0.409

Analysis Plan

Summary statistics will be provided for continuous variables. Frequency tables will be used to summarize categorical variables. Logistic regression will be utilized to assess the effect of patient prognostic factors on the response rate and the toxicity rate. The distribution of time-to-event endpoints will be estimated using the method of Kaplan and Meier. Comparison of time-to-event endpoints by important subgroups will be made using the log-rank test. Cox proportional hazard regression will be employed for multivariate analysis on time-to-event outcomes.

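### The phase I algorithm in section 7 does not state the rule behind Table 2: its escalation factor cannot keep a flagged dose from being used again, and step 1 conditions on Dose 1 but tests T_i

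*Combined protocol and SAP*

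**What the plan says.** The phase I design in section 7.0 uses an independent Beta(0.005, 0.005) prior at each of four doses, target p_T = 0.4, K1 = 1, K2 = 1.5, a flag threshold of 0.95, cohorts of three and at most 18 patients. The first cohort goes to the second of the four doses, which is called Dose Level 1. After each cohort the action with the largest of q(D, i), q(S, i) and q(E, i) is taken, and q(E, i) carries the factor (1 - T_i).

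- Step 1 begins "Suppose that Dose 1 is a dose that has been tried previously" and continues "If $T_i = 1$, terminate the trial due to excessive toxicity".
- Step 2 lets the next cohort go one dose down, stay, or go one dose up. The only limits are at the bottom and the top of the range: "There are two exceptions, however: if $i=1$, the next available doses are" the two lowest, and similarly for the two highest at i = 4. A flagged dose is not among the exceptions.
- Step 3 takes the dose whose posterior mean is nearest the target, "among all the tried doses i for which $T_i=0$ will be selected as the MTD".
- Table 1 prints U beside D, with the legend "U = Current dose is unacceptable".
- Table 2 gives mean total sample sizes of 17.568, 18, 18, 17.979, 18 and 17.16 for Scenarios 1 to 6.

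**The concern.** A safety flag in a dose-finding rule should do two things: end the trial when even the lowest dose is too toxic, and keep later cohorts away from a dose already judged too toxic. As indexed, the text clearly specifies neither. Step 1 names one dose and tests another index. The escalation factor looks at the dose the cohort has just received, where it is redundant, and not at the dose the next cohort would receive.

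If step 1 is taken as a lowest-dose stop, new patients can be sent back to a dose already flagged. If it is taken as a stop on any flag, the trial can end before lower doses are studied. The selected dose carries into phase II, and the phase I patients treated at it are counted there, so the people running the trial need one unambiguous rule, and Table 2 should describe that rule.

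**Working it through.** All results are exact: every path of six cohorts of three was enumerated with the section 7 constants and the six Table 2 scenarios.

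**1. Reproducing Table 2.** With a stop only on T_1 (the lowest dose), the factor (1 - T_{i+1}), and a start at the third dose, mean N is 17.57, 18.00, 18.00, 17.98, 18.00 and 17.00. The printed values are 17.568, 18, 18, 17.979, 18 and 17.16. Mean patients at any dose differ from print by at most 0.26. Selection probabilities agree within 0.027 if posterior means are made monotone first. That is an assumption; section 7 mentions only the posterior mean, and raw means leave differences of up to 0.17.

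Mean patients at Level -1 separate the two forms of the escalation factor (third-dose start):

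| Scenario | Printed | (1 - T_{i+1}) | (1 - T_i) |
|---|---|---|---|
| 1 | 5.799 | 5.70 | 5.23 |
| 2 | 0.432 | 0.40 | 0.05 |
| 4 | 2.073 | 2.03 | 1.54 |

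**2. The factor (1 - T_i) is inert.** If T_i = 1, then P(p_i > 0.4) > 0.95, so before any multiplication q(E, i) is at most P(p_i < 0.4), which is below 0.05. Then q(D, i) + q(S, i) > 0.95, and the larger of the two exceeds 0.95/2 = 0.475. Escalation cannot be the maximum, with or without the factor. Checking every outcome up to 18 patients shows that D is the largest wherever T_i = 1.

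**3. A path that can be checked by hand (Scenario 2, true rates 0.05, 0.1, 0.4, 0.6).**
- First cohort at Level 1, 0 of 3 toxicities: 0.9^3 = 0.729, so escalate (q(E) = 0.999).
- Level 2, 3 of 3: 0.4^3 = 0.064, so the dose is flagged and the trial de-escalates.
- Second cohort at Level 1, 0 or 1 of 3: 0.729 + 3 x 0.1 x 0.81 = 0.972. The totals are 0/6 or 1/6, and both give E (at 1/6, q(E) = 0.647 against q(S) = 0.333).
- The next cohort goes back to the flagged Level 2.

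The probability is 0.729 x 0.064 x 0.972 = 0.045. Table 1 prints the same action at each of these cells.

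**4. All paths, lowest-dose stop, stated start, (1 - T_i) as written.** Probability that at least one further cohort is treated at a flagged dose:

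| Scenario | 1 | 2 | 3 | 4 | 5 | 6 |
|---|---|---|---|---|---|---|
| (1 - T_i) | 0.109 | 0.118 | 0.048 | 0.122 | 0.010 | 0.071 |
| (1 - T_{i+1}) | 0 | 0 | 0 | 0 | 0 | 0 |

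**5. Step 1 read as a stop on any flag, stated start.** Mean N is 13.90, 16.62, 17.54, 16.10, 17.90 and 12.59. Scenarios 1 and 6 are far from the printed 17.568 and 17.16, and further still from a third-dose start (11.84 and 11.32). Under this reading the probability of return to a flagged dose is 0 in every scenario.

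**6. Other mismatches seen in the check.**
- Starting dose: Table 2 shows a mean of 0.315 patients at Dose 1 in Scenario 5. If every trial starts there with a cohort of three, that mean cannot be below 3. Under the corrected indices and the stated start, patients per dose differ from print by up to 4.9.
- Table 1 marks U only where every patient had a toxicity, but the 0.95 threshold also flags 4/5 (0.974), 5/6 (0.990) and 8/12 (0.971).
- Table 1 prints S at 2/3, 3/5 and 4/7, where the stated formula gives D (at 2/3, q(D) = 0.595 against q(S) = 0.403).

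**The case against.** The strongest reply is that the intention is plain and the error is one of notation. Step 1 speaks of Dose 1; Table 1 pairs U with de-escalation; step 3 chooses among unflagged doses, which presumes that a trial can run on after a flag; and the mean sample sizes in Table 2 fit only a lowest-dose stop. The subscript in step 1 may also be a misreading of 1 as i in the PDF text. All of this stands, and for that reason the any-flag figures above serve only to rule that reading out.

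A reader might infer something stronger: that the trial as written stops whenever any dose is flagged and can also send patients back to flagged doses. The documents do not support this. The first excludes the second, and the first is contradicted by both tables and step 3.

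It can also be said that staff would follow Table 1 and not the formula. Using Table 1's own actions and U cells, with a lowest-dose stop and the stated start, return to a U dose still occurs in about 8%, 10% and 9% of trials in Scenarios 1, 2 and 4. The size falls somewhat; the gap remains. Nor does the possible misreading in step 1 help here: the escalation factor would have to have lost a whole +1, while (i+1) is intact in step 2.

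Finally, step 2 makes clear that i = 1 is the lowest dose, so the labelling problem is small: Table 2 heads its columns by level name, and its Dose 1 is i = 2.

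**Conclusion.** The point holds as a mismatch between the text of section 7 and its own tables. The factor (1 - T_i) has no effect, and nothing else in the text keeps a cohort from being escalated to a flagged dose. Under a lowest-dose stop and the stated start this happens in about 11-12% of trials in Scenarios 1, 2 and 4, 7% in Scenario 6, 5% in Scenario 3 and 1% in Scenario 5. Step 1 is internally inconsistent in its index, and its any-dose reading should be set aside.

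It does not follow that Table 2 was produced without these safeguards. It fits the lowest-dose stop with the next dose's flag closely, but from a starting dose other than the one section 7 states.

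The percentages rest on the stated formula, constants and cohort size and on the toxicity rates assumed in Table 2. They are about 8-10% in Scenarios 1, 2 and 4 if Table 1 is followed instead. The correction should be made: it is small, and it decides whether patients can be treated at a dose already flagged.

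**What to change.** - In step 1, refer to T_1 and say that this is the lowest dose (i = 1, Level -1). For a higher flagged dose, refer to the D printed with U in Table 1.
- In q(E, i), replace (1 - T_i) by (1 - T_{i+1}), so that escalation to a dose already flagged has probability zero.
- State once that i = 1, 2, 3, 4 are Levels -1, 1, 2, 3, and use the same labels in Table 2.
- Regenerate Tables 1 and 2 from the reconciled rule and the starting dose that section 7 states, with U marked wherever the 0.95 threshold is crossed. If the text's starting dose is not the one intended, the text and Table 2 must be reconciled first. Say whether posterior means are made monotone before the MTD is selected.

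The cost is two index changes, a line of definitions and one rerun. Because flagged doses are no longer revisited, correct selection falls by about 2-3 points in some scenarios (Scenario 2: from about 70% to 67%).

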6.2 Phase I Portion

To determine the MTD of the combination of thalidomide, lenalidomide and dexamethasone (LTD), with 4 dose levels planned. Dosing will start at doses of LTD that are intermediate intensity because of overlapping side effect profile of lenalidomide and thalidomide to determine the MTD and maximize the overall response rate of the regimen.

Table 6-1 Dose Levels to be studied

Dose Level	Assigned Therapy
Level -1	15 mg Lenalidomide daily on days 1-21 followed by 7-day rest every 28 days 50 mg Thalidomide daily 40 mg dexamethasone *
Level 1	15 mg Lenalidomide daily on days 1-21 followed by 7-day rest every 28 days 100 mg Thalidomide daily 40 mg dexamethasone *
Level 2	25 mg Lenalidomide daily on days 1-21 followed by 7-day rest every 28 days 100 mg Thalidomide daily 40 mg dexamethasone *
Level 3	25 mg Lenalidomide daily on days 1-21 followed by 7-day rest every 28 days 200 mg Thalidomide daily 40 mg dexamethasone

* Dexamethasone dosing for cycle 1-2: 40 mg days 1-4, 9-12, and 17-20; all subsequent cycles: 40 mg days 1,8, 15, 21

Dose Escalation

The first cohort of three patients enrolled into the study will receive dose level 1. A full safety evaluation will be conducted when these subjects have completed one cycle (28 days) of combination therapy.

Definition of DLT

A DLT will be defined as follows:

- Hematologic dose-limiting toxicity will be defined as either Grade 4 neutropenia lasting for ≥ 7 days in duration, any Grade 4 thrombocytopenia, or any Grade 5 hematologic toxicity. At least three patients in each cohort must be evaluable for hematologic toxicity.
- Non-hematologic dose-limiting toxicity will be defined as any Grade 3, 4 or 5 non-hematologic toxicity, with the specific exception of:
 - Isolated Grade 3 elevation of liver function tests (LFTs) without associated clinical symptoms, lasting for ≤ 7 days in duration.
 - Isolated Grade 3 elevation of amylase without associated clinical symptoms
 - Grade 3 hypocalcemia, hypokalemia, hypomagnesemia, hyponatremia, or hypophosphatemia which responds to medical intervention.

Definition of Maximum Tolerated Dose:

The MTD of the combination of lenalidomide, thalidomide and dexamethasone in multiple myeloma subjects shall be defined at the end of the trial, the dose with the smallest absolute value of (*posterior mean of pi-pT*) among all the tried doses *i* for which $T_i=0$ will be selected as the MTD.

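### The MTD selection rule ignores dose order, so a lower dose can be selected because it had more DLTs, or fewer patients, than a better-tolerated higher dose

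*Combined protocol and SAP*

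**What the plan says.** Section 7.0, Phase I design, treats each dose separately: "Assuming a vague independent beta prior $B(0.005, 0.005)$ for each p_i". With x DLTs in n patients the posterior is Beta(0.005 + x, 0.005 + n − x). The target toxicity p_T is 0.40. A dose is flagged (T_i = 1) when the posterior probability that its toxicity exceeds 0.40 is above 0.95.

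Step 3 then gives the selection rule: "At the end of the trial, the dose with the smallest absolute value of" the posterior mean minus 0.40, "among all the tried doses i for which $T_i=0$ will be selected as the MTD". Section 6.2, Definition of Maximum Tolerated Dose, repeats the rule: the MTD "shall be defined at the end of the trial, the dose with the smallest absolute value of" the same difference. Neither place orders the estimates by dose or says what to do with ties. Dose order enters only in step 2, which moves cohorts up or down.

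For the case where every dose is below the target (Scenario 5), section 7.0 says that "the highest dose will be chosen with the highest probability and most patients will be treated at the highest dose". Table 2 gives that selection probability as 0.881.

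**The concern.** Distance from 0.40 is a sensible criterion only if the estimates rise with dose. With independent raw estimates from 3 to 12 patients per dose, inversions are common. When all the estimates are below 0.40, the nearest one is the largest, whatever dose it belongs to. Good tolerability at a higher dose then counts against that dose, and one chance DLT at a lower dose counts in favour of the lower dose. The flag T_i does not help, because it removes only doses that look too toxic.

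The MTD is the phase I primary objective. It also sets the phase II regimen, and the phase I patients treated at it become the first phase II patients, so a wrong selection carries into the phase II primary analysis.

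**Working it through.** **Inputs (section 7.0).** Beta(0.005, 0.005) prior per dose; p_T = 0.40; ξ = 0.95; cohorts of three; at most 18 patients; start at Dose Level 1, the second of four doses; actions from Table 1; true rates from Table 2.

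**Posterior mean.** m = (x + 0.005)/(n + 0.01).

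**Hand check 1: no DLT in 18 patients.** Table 1 escalates after 0/3 at Level 1 and 0/3 at Level 2, and the other 12 patients are treated at Level 3.

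- Levels 1 and 2: m = 0.005/3.01 = 0.00166; distance from 0.40 is 0.39834.
- Level 3: m = 0.005/12.01 = 0.00042; distance is 0.39958.

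Levels 1 and 2 tie, and Level 3 loses only because more patients tolerated it.

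**Hand check 2: 1/6 at Level 1, 0/3 at Level 2, 1/9 at Level 3.** Table 1 allows this path: 1/3 stay, 1/6 escalate, 0/3 escalate, then three cohorts at Level 3.

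- Level 1: 1.005/6.01 = 0.16722; distance 0.23278.
- Level 2: 0.005/3.01 = 0.00166; distance 0.39834.
- Level 3: 1.005/9.01 = 0.11154; distance 0.28846.

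Level 1 is selected. Levels 1 and 3 have one DLT each, and Level 3 has the lower rate in more patients. Under pool-adjacent-violators all three doses pool to 2.015/18.03 = 0.1118, which no longer favours the lower dose.

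**Enumeration.** Every six-cohort path was enumerated exactly with Table 1 actions and no re-entry to flagged doses. Each outcome was scored by the rule as written (ties to the lower dose, then to the higher) and by isotonic posterior means with weights n + 0.01.

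| Scenario (dose scored) | As written, ties down to ties up | Isotonic |
|---|---|---|
| 1 (dose at 0.40) | 52.6% to 50.7% | 54.7% |
| 2 (dose at 0.40) | 64.8% to 66.2% | 68.7% |
| 3 (dose at 0.40) | 66.2% to 66.8% | 72.5% |
| 4 (dose at 0.35) | 64.5% to 64.2% | 63.2% |
| 5 (highest dose, 0.20) | 60.4% to 61.8% | 84.8% |
| 6 (dose at 0.60) | 21.5% to 24.0% | 18.7% |

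In Scenario 6 every dose is above the target, so a lower figure is better.

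In Scenario 5 the selected dose lies below an acceptable tried dose with a strictly lower DLT rate in 21.1% of trials. Equal rates add 3.2% to 5.2%, giving 24% to 26%. Strict inversions are about 9% in Scenario 3, 2% in Scenario 2, 1% in Scenario 4, and about 0 in Scenarios 1 and 6.

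**Formulas instead of the printed chart.** At multiples of three patients the two differ only at 2 DLTs in 3 patients (chart: stay; formula: de-escalate). With the formula actions, Scenario 5 goes from 59-61% to 83%.

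**Against Table 2.** The printed 0.881 for Scenario 5 is not reproduced by the written rule. From the stated start it gives at most 0.62; from a third-dose start it gives 0.69 to 0.74. Table 2 also lists 0.315 and 0.48 patients at Dose 1 in Scenarios 5 and 3, which is impossible if the first three patients are treated there. The closest match found was a third-dose start with isotonic selection: 0.895 for Scenario 5, and a largest difference of 0.023 in any selection probability.

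**The case against.** Four points deserve weight.

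- **Timing.** Section 6.3 says the added lenalidomide-refractory cohort is treated at the MTD regimen and names its doses. Its lenalidomide and thalidomide doses match Level 2, so the selection has probably been made. Changing the rule now is post hoc, and without the data nobody can say that an inversion occurred. This stands. It bears on how a re-run is reported, not on whether the rule is sound.
- **Scenario 5 has no dose at the target.** The move from 60% to 85% measures selection of the top dose, not of a true MTD, and gains elsewhere are only a few points. This is a fair limit. But Scenario 5 is the plan's own scenario, with a stated expectation that the highest dose is chosen, and Scenario 3 gains about 6 points.
- **The examples are rare, and effects are mixed.** In Scenario 5 the two hand-check outcomes have probabilities 3.1% and 3.3%, and the 24-26% includes equal rates. Both are true, but strict inversions alone total 21%. In Scenario 6 about half of the fall from 24.0% comes from the tie rule.
- **It may be an omission in the text.** The Table 2 simulations look closer to an order-restricted rule, and an order-constrained inference paper is item 24 in the reference list. That is an inference: the text neither cites nor applies that paper, and step 3 is the rule that would be followed.

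**Conclusion.** The concern holds. As written, step 3 and section 6.2 can select a lower dose because it had more DLTs, or fewer patients, than a better-tolerated higher dose. This follows from the written formula, and the hand-check outcomes are reachable under Table 1.

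The size depends on true toxicity. The effect is large when the tried doses are truly below 0.40 (Scenario 5), moderate in Scenario 3, small in Scenarios 1 and 2, and slightly reversed in Scenario 4. Table 2's 0.881 cannot be cited in support of the written rule.

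The enumeration assumes the stated start, Table 1 actions and no re-entry to flagged doses. Allowing re-entry barely changes Scenario 5 (61-62% as written, 85% isotonic). No view is taken on which dose is clinically right. Because the rule decides the phase I primary result and the phase II dose, it must be corrected.

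**What to change.** In section 7.0 step 3 and in section 6.2, state that isotonic regression (pool-adjacent-violators, weights n_i + 0.01) is applied to the posterior means of the tried doses, and that the MTD is the T_i = 0 dose whose isotonic mean is nearest 0.40. Add a tie rule: the highest tied dose if the pooled mean is at or below 0.40, otherwise the lowest. Other weights or tie rules could be defended; what matters is that one is stated.

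Re-run Table 2 with the stated start and the stated rule. If an order-restricted rule was used in the existing simulations, say so. If phase I data are in, re-run the selection on them, report both results, and label the second as made after the data were known.

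The cost is two sentences, a few lines of code and no patients. The one statistical loss found is about one point of selection probability in Scenario 4 (64.5% to 63.2%).

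### Phase I operating characteristics (Table 2) cannot come from the stated Dose Level 1 start, and the accompanying text contradicts the printed figures for Scenarios 1 and 6

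*Combined protocol and SAP*

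**What the plan says.** The starting dose is stated consistently. Section 6.2 (Phase I Portion) says: "The first cohort of three patients enrolled into the study will receive dose level 1". Section 7.0 repeats it twice, the second time as "Starting at Dose Level 1 (the second dose), the trial will enrol patients in a cohort size of three". Dose Level 1 is the second of four doses, labelled -1, 1, 2 and 3.

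Step 2 of the algorithm in Section 7.0 allows one level down, no move, or one level up: "the decision to select the dose for next cohort are among" these neighbouring doses. The maximum is 18 patients, the target toxicity is 0.4, and each dose has a Beta(0.005, 0.005) prior, with K1 = 1, K2 = 1.5 and ξ = 0.95.

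Section 7.0 then describes Table 2 in words:
- For Scenarios 1 to 3, where one dose is the MTD: "the number of patients treated at this dose will be the largest among all doses".
- For Scenario 5, where all doses are below target: "most patients will be treated at the highest dose".
- For Scenario 6, where all doses are too toxic: "the chances of these doses being selected are very low and most of the few patients treated will be at the lowest dose level".

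**The concern.** If the first cohort of three is always at Dose Level 1, no trial can have fewer than three patients there, so a mean below 3 cannot arise. Table 2 prints two such means. Separately, the statements on Scenarios 1 and 6 do not match the rows they describe.

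Table 2 and its text are the only performance evidence given for the 18-patient Phase I. A reader relies on them for two things: how often a tolerable top dose would be found, and how well the design protects against recommending a dose that is too toxic. The text reassures on the second where the printed figures do not.

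**Working it through.** **1. The printed rows are intact.** Scenario 3: 0.012 + 0.48 + 7.164 + 10.344 = 18.000. Scenario 5: 0.03 + 0.315 + 5.991 + 11.664 = 18.000. Both equal the printed totals, so a broken table does not explain the values.

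**2. Lower bound at Dose Level 1.** One cohort of three is always treated there, so the mean is at least 3.0. Printed: 0.48 and 0.315. Dose 2 is the only column with at least 3 patients in all six scenarios.

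**3. Upper bound at the top dose, Scenario 5** (toxicity 0.05, 0.10, 0.15, 0.20). From Level 1 the top dose can receive at most four of six cohorts, or 12 patients. That requires the first cohorts at Levels 1 and 2 both to escalate, which needs 0/3 DLTs in each under Table 1 and the formula alike. The probability is 0.9³ × 0.85³ = 0.729 × 0.614 = 0.448. Otherwise the maximum is 9. The mean is therefore at most 12 × 0.448 + 9 × 0.552 = 10.34. Printed: 11.664.

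**4. Text against the printed table.**
- Scenario 1: the MTD (Dose -1) treats 5.799 patients and Dose 1 treats 6.069.
- Scenario 6: the probability that some over-toxic dose is selected is 0.492 + 0.233 + 0.078 + 0.004 = 0.807. Patients treated: 17.16 of 18. Share at the lowest dose: 6.216 / 17.16 = 36%, the largest share but not a majority.

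**5. Attempt to reproduce Table 2.** All six-cohort paths were enumerated exactly, reading step 1 as stopping when the lowest dose is flagged unacceptable. With the formula's moves and flag:
- Level 1 start: the largest gap from the 24 printed counts is 4.85 to 4.89 patients.
- Dose 2 start: the largest gap is 0.40 (0.60 if re-escalation to a flagged dose is allowed). Scenario 5 gives 0.01 / 0.32 / 5.75 / 11.92 against the printed 0.03 / 0.315 / 5.991 / 11.664.
- The match is not complete: in Scenario 2 at Dose -1 it gives 0.05 against 0.432 printed.

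**6. Where the rules are unsettled.**
- (a) At 2 DLTs in 3 patients Table 1 prints S. The formula gives D, with q(D) = 0.595 and q(S) = 0.403. At multiples of three this is the only difference in moves.
- (b) Table 1 prints U only where every patient has a DLT. The formula gives T = 1 also from 5/6, 6/9, 8/12, 10/15 and 11/18 upward.
- (c) The plan does not say whether escalating back to a tried dose with T = 1 is barred.

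**7. Results from the stated start.** Ranges cover the options in (a) to (c), except that the count of 4.41 to 4.56 is for the formula's T. No tie-break is given for the final selection; that choice moves the selection figures by less than 0.02.

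| Quantity | Printed | Level 1 start |
|---|---|---|
| Mean at Dose Level 1, Scenarios 3 and 5 | 0.48, 0.315 | 4.41 to 4.56 |
| Share at top dose, Scenario 5 | 65% | 45 to 47% |
| Top dose selected, Scenario 5 | 0.881 | about 0.59 to 0.62 |
| Top dose selected, Scenario 3 | 0.765 | about 0.64 to 0.70 |
| Dose 2 or 3 selected, Scenario 4 | 0.322 + 0.025 = 0.347 | 0.21 to 0.27 |
| Any dose selected, Scenario 6, formula T | 0.807 | 0.72 to 0.75 |
| Any dose selected, Scenario 6, Table 1 U | 0.807 | 0.89 to 0.90 |

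Two statements depend on the reading. With the formula's T, the claim that the MTD has the largest count in Scenario 1 holds under formula moves with the bar (8.51 against 7.85). It fails without the bar (8.11 against 8.18) and under Table 1 moves (6.95 against 9.51 with the bar, 6.44 against 9.93 without). With Table 1's U flags and formula moves it holds even without the bar (8.43 against 8.18). In Scenario 6 with the formula's T, the lowest dose has 55 to 57% of patients under formula moves and 44 to 46% under Table 1 moves.

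**The case against.** The strongest reply is that little turns on this. Section 6.3 already names an MTD regimen for the additional lenalidomide-refractory cohort, with the lenalidomide and thalidomide doses of Level 2, so a rerun would probably change no dose assignment. The Section 7.0 expectation of at least 6 patients at the MTD is also not undermined: with the formula's T, the mean at the true MTD from the stated start is 6.4 to 8.5, 9.3 to 9.8 and 7.0 to 7.9 in Scenarios 1 to 3. The claim that the Scenario 1 MTD has the highest selection probability agrees with the table (0.507). And a reader can see 0.492 and 17.16 beside the text that misdescribes them. All of this stands and limits the consequence; none of it makes the figures right.

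One might read the Scenario 6 sentence dose by dose, not as a total. That does not rescue it, since Dose -1 alone has 0.492.

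A reader might also infer that the design is less safe than printed. The results do not support that as a general statement: over-toxic selection in Scenario 4 is lower than printed, and the direction in Scenario 6 depends on which unacceptable-dose flag is used.

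**Conclusion.** Wrong as written. The Dose Level 1 counts in Scenarios 3 and 5 and the Scenario 5 top-dose count are impossible under the stated start. This needs only the starting dose, the cohort size, one-level moves and, for the top dose, the printed toxicity rates. The Scenario 1 count statement and all three parts of the Scenario 6 statement contradict the printed table, whatever its origin.

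Two statements also fail from the correct start under every reading examined: a very low chance of selection in Scenario 6 (at least 0.72) and a majority at the highest dose in Scenario 5 (45 to 47%). The correction is unfavourable for reaching and selecting a tolerable top dose and favourable on over-dosing in Scenario 4. The recomputed figures assume step 1 refers to the lowest dose.

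Three stronger readings are not supported:
- That Table 2 was run from Dose 2. This is an inference from similar counts; the simulated algorithm is not fully recovered.
- That the starting dose explains the whole Scenario 5 selection gap. A Dose 2 start with the formula and the written selection rule gives 0.69 to 0.72, still short of 0.881.
- That patients would start at the wrong dose or that the wrong MTD was named. Every statement of the starting dose says Dose Level 1, and the documents give no Phase I results.

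**What to change.** First settle, in Section 7.0:
- the action at 2 DLTs in 3 patients (Table 1 or the formula);
- the unacceptable-dose flag (Table 1's U cells or the formula's T = 1), with Table 1 corrected to match if the formula governs;
- whether escalation to a tried dose with T = 1 is barred.

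Then rerun Table 2 from Dose Level 1 with those rules and the final selection rule the trial actually uses, including a tie-break, and rewrite the text from the output. The claim of very low selection chances in Scenario 6 and the claim of a majority at the highest dose in Scenario 5 should go in any case. Keep the largest-count claim for Scenario 1, and the few-patients and lowest-dose-majority claims for Scenario 6, only if the rerun supports them. Do not insert a replacement percentage for Scenario 6 beforehand: the flag alone moves it from 0.72 to 0.75 up to 0.89 to 0.90.

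The cost is a short simulation and revised wording, with less favourable figures for Scenarios 3 and 5. No patients are added, and the planned dose levels and sample size stay as they are.
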